5.7 INFORMATION SHEET ON COVID-19

In light of the circulating severe acute respiratory syndrome Coronavirus-2 (SARS-CoV-2) and the associated coronavirus disease (COVID-19) pandemic, the clinic will provide to the participant at time of consent an information sheet regarding proposed modifications put in place to safeguard the health and well-being of participants. The modifications provide flexibility for conducting study visits and procedures when needed to monitor participant safety. These modifications are expected to be time-limited in relation to the COVID-19 pandemic. In consultation with the Sponsor and MHRP, the study team will determine when, in the future, the guidance is no longer applicable. WRAIR and SERU will be notified when such a determination is made.

6 LABORATORY ASSESSMENTS

6.1 BLOOD SAMPLES

After collection, all specimens will be transported to the site laboratory according to a standard operating procedure (SOP). Samples will be packaged in appropriate isothermal containers for transportation. On arrival at the laboratory, all specimens will be logged into a sample tracking database before distribution to the different assay benches for processing.

Blood processing is performed using Good Clinical Laboratory Practices (GCLP), with personal protective equipment, including lab coats, gloves, and laminar flow hoods. All specimens will be labeled with barcode indicating participant identification numbers (PID), sample type, date and study visit number and will be indexed and cross-referenced in a specimen-tracking database. The processing lab staff will only know the PID to ensure confidentiality.

Blood collected for plasma or serum specimens will be centrifuged, aliquoted, and stored at -70°C or colder. PBMCs will be isolated, cryopreserved and stored in the vapor phase of a liquid nitrogen freezer. Mucosal Specimens will be processed according to standard laboratory operating procedures and stored -70°C or colder freezer. All specimens will be labeled with barcode indicating: PID, sample type, date and study visit number and will be indexed and cross-referenced in a specimen-tracking database. These procedures are detailed in the laboratory MOP.

6.1.1.1 Laboratory tests to assess safety

Clinical laboratory testing will take place in the CAP-certified laboratory and includes pregnancy testing, complete blood count, chemistry (Creatinine, ALT, AST) and HIV testing. HIV testing will be performed according to the approved laboratory algorithm including 4th generation immunoassay and nucleic acid testing when indicated. Safety labs may be repeated if clinically indicated.

6.1.2 IMMUNOGENICITY TESTS

Cryopreserved samples will be shipped to laboratories at MHRP/WRAIR, Armed Forces Research Institute of Medical Sciences (AFRIMS) or other laboratories listed to perform the assays listed below. Additional assays/analytes may be added that fall into the categories described in the schedule of events.

6.1.2.1 HIV-1-specific binding antibody assays

Binding antibody assays will be performed to detect serum, plasma, or mucosal secretion binding antibodies to a broad array of HIV-1 antigens. Serum and plasma will be also tested for their ability to block HIV-1 binding to the $\alpha 4\beta 7$ receptor and other possible HIV-1 co-receptors. In addition, antibody isotype, subclass, FC gamma, complement usage, and other antibody profiling tools may be utilized in parallel with antigen specificity. Monoclonal antibodies may also be isolated from selected vaccine recipients.

6.1.2.2 Functional antibody assays

Antibody-dependent Cell-Mediated Cytotoxicity (ADCC) Assay and Antibody-dependent Cell-Mediated Viral Inhibition (ADCVI) Assays: ADCC assays will be performed at visits specified in the SOE using rapid fluorometric ADCC assay. Other functional assays may include but are not limited to Antibody-dependent Cell-Mediated Phagocytosis (ADCP) and Antibody-dependent Complement (ADC) activation assays.

6.1.2.3 Neutralizing antibody assays

Neutralization assays will be performed similarly to other HIV vaccine trials using cell line-based and PBMC assays with a panel of viruses from different HIV subtypes, including A, B, C, D, and other circulating recombinant forms (CRFs) such as AE and AG.

6.1.2.4 Cellular immune assays

Cryopreserved PBMC and lymph nodes will be stimulated with HIV-1-specific antigens and tested using standard (but not limited to) cellular immune assays which may include but are not limited to Intracellular Cytokine Staining, ELISPOT, Lymphoproliferation assays, B-cell analysis, T-follicular helper cell, and innate immune cell analysis

6.1.3 OTHER ASSAYS

- Gene expression/transcriptomic analysis using current technologies.
- Genetic analysis including but not limited to Human Leukocyte Antigen (HLA) subtyping.
- Soluble factor/cytokine analysis: Levels of soluble inflammatory markers will be evaluated representing different biological pathways such as general inflammation, tumor necrosis factor- α (TNF- α) signaling, IFN- γ signaling, and lymphocyte activation. Additional markers may be included.
- Sequencing of HIV-1 RNA to characterize viral features and assess the effect of the vaccine if a volunteer becomes infected with HIV-1 during the study.

6.2 FUTURE USE AND STORAGE OF BIOLOGICAL SAMPLES

Each study participant will be asked to voluntarily consent to their blood samples to be stored for other research studies that may be done after this study is complete. Future testing may involve genetic tests. In case the participant is unwilling to have their biological samples stored for future use, they can consent to participate in this study only, without having their blood samples stored for future testing. In this case, their blood samples will be destroyed within one year of receiving notification from the protocol chair that all protocol testing is complete. Samples remaining in the KEMRI/USAMDR-A CRC repository will be destroyed by laboratory staff following approved laboratory procedures.

All samples for which consent has been obtained and for which additional material is available after study specified testing is complete will be stored for future testing at the KEMRI/USAMRD-A CRC Laboratory in Kericho. However, KEMRI SERU and WRAIR IRB approval will be sought before any such samples are used for analysis not specified in the protocol or a protocol amendment approved by the IRB. All samples belong to the site from which they were obtained and MHRP.

During the study, blood samples will be tested soon after collection. The remaining samples will then be stored at the KEMRI/USAMRD-A CRC lab. For specialized tests that are not available at this site some of the blood samples will be shipped to the United States for HIV immune response testing as well as genetic testing. Shipment of these samples will be done only after the approval of the KEMRI SERU.

7 DATA MANAGEMENT AND ANALYSIS

7.1 STUDY DOCUMENTATION, STORAGE, AND DATA COLLECTION

Signed Informed Consent Forms (ICFs) and study documents are kept in a room that is double locked with limited access. The investigators and staff are responsible for ensuring maintenance of a comprehensive centralized filing system of all study-related (essential) documentation, suitable for inspection at any time by the following organizations will be granted direct access to the participant's original medical records: KEMRI SERU, Kenya PPB, the Kenya Ministry of Health, NIAID, US FDA, WRAIR, USAMRDC, ORP, HRPO, and the people who work for these organizations, and other local, US or international regulatory agencies. Participants information may also be reviewed or inspected for verification of clinical trial procedures and or data. Inspections will be conducted without violating the confidentiality of the participant, to the extent permitted by the applicable laws and regulations and that, by signing a written informed consent form, the participant is authorizing such access.

Data will be collected using source documents and or Case Report Forms (CRFs). Direct entry using tablets or computers is possible depending on the current site capability. Data will be uploaded daily to the central DCAC database. Access to the data collection software is limited to PI approved staff and requires unique usernames and passwords. Data are housed in a secure database maintained by the DCAC, MHRP in accordance with Good Clinical Practices (GCP). Study data are referenced only by the study-specific identification code. The study records will be stored at the KEMRI/USAMRD-A triple-locked filing room for the period when the study is active, and thereafter transferred to the site's archive for long term storage. All participants consented will be assigned a 7-digit Participant Identification (PID). Participant IDs will be assigned sequentially, for example 460-0001.

7.2 ANALYSIS

7.2.1 POWER AND SAMPLE SIZE

The safety, reactogenicity, and tolerability of the vaccine regimens are the primary endpoints for this study. Below in Table 6, the estimated probability of a participant having at least one of these events (in percent), along with the associated exact Clopper-Pearson 95% confidence interval, is given for various numbers of observed events that correspond to approximate event rates within study groups of possible interest. Note that some event rates cannot be exactly observed within a given group, depending on the sample size (e.g. 10% of 15 participants is 1.5 participants, which is rounded to 2 in the table below).

Table 5: Estimated probability (in percent) of a participant having at least one AE, along with the associated exact Clopper-Pearson 95% CI, given varying sample sizes and numbers of participants with at least one observed AE

Group	n	Approximate AE Rate ¹							
		0%		10%		20%		50%	
		Corresponding # AEs ²	Estimated Probability (95% CI)	Corresponding # AEs ²	Estimated Probability (95% CI)	Corresponding # AEs ²	Estimated Probability (95% CI)	Corresponding # AEs ²	Estimated Probability (95% CI)
Each Individual Group	15	0	0 (0, 21.8)	2	13.3 (1.7, 40.5)	3	20 (4.3, 48.1)	8	53.3 (26.6, 78.7)
Placebo	21	0	0 (0, 16.1)	2	9.5 (1.2, 30.4)	4	19 (5.4, 41.9)	11	52.4 (29.8, 74.3)
Any DNA Prime with HIV Env gp145 C.6980 /Rehydragel Boosts	105	0	0 (0, 3.5)	11	10.5 (5.3, 18.0)	21	20 (12.8, 28.9)	53	50.5 (40.5, 60.4)
DNA alone (1+2), DNA+TCI (3+4), DNA/ALF43 (5+6)	30	0	0 (0, 11.6)	3	10 (2.1, 26.5)	6	20 (7.7, 38.6)	15	50 (31.3, 68.7)
HIV Env gp145 C.6980 /Rehydragel boost (1+3+5), HIV Env gp145 C.6980 /Rehydragel/ALF43 boost (2+4+6)	45	0	0 (0, 7.9)	5	11.1 (3.7, 24.1)	9	20 (9.6, 34.6)	23	51.1 (35.8, 66.3)
Any ALF43	75	0	0 (0, 4.8)	8	10.7 (4.7, 20.0)	15	20 (11.6, 30.8)	38	50.7 (38.9, 62.4)

¹ The approximate proportion of participants in a group reporting at least one event of interest

² The number of participants with observed event(s) needed to most closely correspond to the given approximate event rate, with the given sample size

For illustration, if 2 individuals among the 15 participants in an individual vaccine group experienced at least one event, the estimated event probability would be 13.3%, with an associated exact 95% CI of (1.7%, 40.5%). Eleven individuals reporting at least one event among all active participants (n=105) would lead to a similar estimated event probability of 10.5%, but with a narrower exact 95% CI (5.3%, 18%).

The table below gives the probability of observing at least one or more than one event in a group of interest, given underlying per-subject probabilities of at least one event.

Table 6: Probability of observing at least one or at least two safety events in a given group, given varying underlying per-participant probabilities of experiencing at least one event

Group	n	Underlying Probability of At Least One Event					
		1%		10%		20%	
		>0	>1	>0	>1	>0	>1
Each Individual Vaccine Group	15	14.0%	1.0%	79.4%	45.1%	96.5%	83.3%
Placebo	21	19.0%	1.9%	89.1%	63.5%	>99%	94.2%
Any Env-C Plasmid DNA Prime with HIV Env gp145 C.6980 /Rehydragel Boosts	105	65.2%	28.3%	>99%	>99%	>99%	>99%
Env-C Plasmid DNA alone (1+2), Env-C Plasmid DNA+TCI (3+4), Env-C Plasmid DNA/ALF43 (5+6)	30	26.0%	3.6%	95.8%	81.6%	>99%	>99%
HIV Env gp145 C.6980 /Rehydragel boost (1+3+5), HIV Env gp145 C.6980 /Rehydragel/ALF43 boost (2+4+6)	45	36.4%	7.5%	>99%	94.8%	>99%	>99%
Any ALF43	75	52.9%	17.3%	>99%	>99%	>99%	>99%

7.2.2 PRIMARY ANALYSIS

The primary endpoints of this Phase 1 study are related to the safety, reactogenicity and tolerability of the Env-C Plasmid DNA vaccine regimens. These will be monitored by PSRT and SMC as appropriate, and SAE), AEs and PIMMC will be recorded until the end of the trial.

SAEs, AEs, AESIs, reactogenicity, and tolerability will be tabulated by study group and combinations of interest. Exact 95% Clopper-Pearson confidence intervals will be calculated for each set of events, and the maximum severity and relatedness will be reported for each participant. While the study was not designed with the purpose of detecting safety differences, comparisons between regimens or between groups of interest and the placebo controls may be made. These comparisons would be made at a two-sided $\alpha=0.05$ level, using the normal approximation to the binomial distribution (z-test) as mentioned in the previous section, or an alternate testing procedure as appropriate (e.g. Fisher's Exact test for smaller samples). No adjustments for multiple comparisons will be made.

7.2.3 SECONDARY ANALYSIS

The secondary endpoints of this study involve the immune response to the vaccination regimens in either the systemic and mucosal compartments. The laboratory assays used to measure these various immune response endpoints typically result in continuous measurements for each participant.

For each continuous immune response variable of interest, means, medians, ranges and 95% Wald confidence intervals will be computed. Proportions and exact 95% Clopper-Pearson confidence intervals will be computed for any categorical variables.

Comparisons of these endpoints between study groups may be made using non-parametric Mann-Whitney U tests, and once again, no adjustments for multiple comparisons will be made due to the hypothesis- generating nature of the study. The groups will be the same as used for the safety comparison but also may include other groups. For any categorical secondary endpoints, Fisher's Exact tests or asymptotic tests assuming normality will be used as appropriate.

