2.5 STUDY DESIGN

The RV460 trial is an exploratory study that will assess the safety, tolerability, and immunogenicity of different adjuvant formulations in combination with an Env-C Plasmid DNA and HIV Env gp145 C.6980 protein in a prime-boost combination. Enrolled participants will receive 3 doses of Env-C Plasmid DNA as a prime (with or without adjuvants) or admixed with HIV Env gp145 C.6980 protein. The Env-C Plasmid DNA is given alone, formulated with the adjuvant ALF43 (Army Liposome Formulation with Monophosphoryl Lipid A (MPLA) and 43% Cholesterol) adjuvant, or co-administered with the transcutaneous adjuvant dmLT (*E. coli* heat labile enterotoxin) applied at the injection site. The HIV Env gp145 C.6980 protein boost will be mixed with ALF43, Rehydragel® or ALF43 plus Rehydragel®.

Study groups will be assessed for HIV-1 Env-specific antibodies responses elicited by boosting with HIV Env gp145 C.6980 protein adjuvanted with Rehydragel® with or without ALF43. Group 7 will assess whether or not the concept of co-delivery of Env-C Plasmid DNA and HIV Env gp145 C.6980 protein simultaneously will increase the frequency and magnitude of immune responses than Env-C Plasmid DNA given IM alone (after first three vaccinations – Study groups 1 and 2 or as an Env-C Plasmid DNA IM prime, protein IM boost combination as was observed in mice and non-human primates [18], [19, 92, 93].

Table 1: Study Design

Group	n =		Prime at weeks 0, 4, 12	Boost at weeks 20, 32, 56
	V	p		
1	15	3	Env-C Plasmid DNA (2 mg, IM)	HIV Env gp145 C.6980 protein (100 µg, IM)/Rehydragel® (500 µg, IM)

Group	n =		Prime at weeks 0, 4, 12	Boost at weeks 20, 32, 56
	V	p		
2	15	3	Env-C Plasmid DNA (2 mg, IM)	HIV Env gp145 C.6980 protein (100 µg, IM)/Rehydragel® (500 µg, IM)/ALF43 (200 µg, IM)
3	15	3	Env-C Plasmid DNA (2 mg, IM) + dmLT (50 µg, TCI)	HIV Env gp145 C.6980 protein (100 µg, IM)/Rehydragel® (500 µg, IM)
4	15	3	Env-C Plasmid DNA (2 mg, IM) + dmLT (50 µg, TCI)	HIV Env gp145 C.6980 protein (100 µg, IM)/Rehydragel® (500 µg, IM)/ALF43 (200 µg, IM)
5	15	3	Env-C Plasmid DNA (2 mg, IM)/ ALF43 (200 µg, IM)	HIV Env gp145 C.6980 protein (100 µg, IM)/Rehydragel® (500 µg, IM)
6	15	3	Env-C Plasmid DNA (2 mg, IM)/ALF43 (200 µg, IM)	HIV Env gp145 C.6980 protein (100 µg, IM)/Rehydragel® (500 µg, IM)/ALF43 (200 µg, IM)

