5.3 ENROLLMENT AND RANDOMIZATION

There will be 18 participants per group (15 vaccine recipients and 3 placebo recipients). Investigators will be blinded to vaccine versus placebo within each group but not across groups. Participants will be block randomized. Group 1 (with a prime of Env-C Plasmid DNA IM alone at weeks 0, 4, 12) will be fully enrolled first. After the 18 participants in Group 1 are enrolled, the remaining groups, 2-7, will begin enrolling participants. Once 24 participants in Groups 2-7 have been enrolled (four from each group) and received their first vaccinations, enrollment and vaccinations in Groups 2-7 will be paused for the time it takes the PSRT to review (typically 3 to 14 days) blinded safety data from these 24 participants covering the period immediately after their first vaccination through Day 7. If it is determined to be necessary by the PSRT, the MHRP SMC will be consulted to review unblinded data to provide a recommendation on continuing enrollment.

When safety has been confirmed with PSRT review, the remaining 14 participants in each of Groups 2-7 will be enrolled, and vaccinations will continue until the first 24 participants in Groups 2-7 (four per group) have received their first boost dose (at 20 weeks—to create a time gap between boost vaccinations of the first cohort and the remaining study participants).

A second scheduled pause (this pauses boost vaccinations only; prime vaccinations can continue) will occur for Groups 2-7 after the same set of participants reviewed during the first scheduled pause (the first 24 participants (four per group) from Groups 2-7) has received its first boost (Group 1 can continue receiving vaccinations). This pause will review blinded safety data from these 24 participants, covering the period from the first boost through Day 7 after that boost. At both scheduled pauses, the PSRT will consult the SMC regarding the pause if either of the following conditions are met: 1) one (or more) participants experience an SAE that is related to a study agent, or 2) two (or more) participants experience grade 3 or 4 AEs of the same type (e.g. elevated ALT) related to a study agent. Boost vaccinations for Groups 2-7 will resume once safety data from the booster sentinel cohort have been reviewed by the PSRT and they have concluded it is safe to proceed.

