5.6 OPTIONAL PROCEDURES

5.6.1 MUCOSAL COLLECTIONS

Participants will have the option of participating in separately consented mucosal collections. These collections will be conducted at the Kericho site at baseline and subsequent intervals per the SOE. Every effort will be made to have the procedures begin early, and in the event that this is not achieved, the procedures will be split and done over two consecutive days, within the study visit window.

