5.6.1.1 Female Participants

Female participants may choose to undergo in cervicovaginal secretion and or rectal sponge secretion collections. Rectal secretions will be collected by rectal sponges by use of a rectal speculum and 2-4 sponges are inserted into the rectum mucosa for at least 4 minutes. The collected sponges will be placed in a sterile conical tube and shipped to the lab for processing. Consenting women will be instructed on how to use a Softcup device to collect cervicovaginal secretions. The cup will remain in place for 4-12 hours. Women that consent for cervicovaginal secretion collection will undergo a PAP smear test at screening. A urine pregnancy test will be done prior to each collection. Pregnant women and those with a history of toxic shock syndrome will be excluded. Date of last menstrual period will be recorded at each collection visit. The collection will not take place if the woman is menstruating or has symptoms of active inflammation or

infection of the vagina or cervix. Rectal sponge secretions will also be collected however will be deferred if there are signs or symptoms of perianal inflammation. Participants will be asked to refrain from penetrative sex up to 72 hours prior to Softcup or sponge placement.

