5.6.1.2 Male Participants

Male participants may participate in semen collection and or rectal sponge secretion collections. Consenting men will be asked to ejaculate into a sterile container for semen collection. Rectal secretions will be collected by rectal sponges by use of a rectal speculum and 2-4 sponges are inserted into the rectum mucosa for at least 4 minutes. The collected sponges will be placed in a sterile conical tube and shipped to the lab for processing. Rectal sponge secretions will also be collected at this visit if the participant agrees. Semen and rectal sponge collections will be deferred from men if there are signs or symptoms of urethral or perianal inflammation, respectively. Participants may participate in semen collection and or rectal sponge secretion collections.

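### The 95% Wald intervals fixed for continuous immune readouts cover only about 93% in a 15-person group; name t-based intervals instead

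*Protocol*

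**What the plan says.** Section 7.2.3 fixes the summary of the immune endpoints: "For each continuous immune response variable of interest, means, medians, ranges and 95% Wald confidence intervals will be computed". It gives no critical value and no measurement scale. The same section uses exact Clopper-Pearson intervals for proportions, allows Mann-Whitney tests between groups, and allows Fisher's exact test for categorical endpoints. On the analysis sets it says: "The groups will be the same as used for the safety comparison but also may include other groups".

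The sizes come from elsewhere in the protocol. Section 5.3 puts 15 vaccine and 3 placebo recipients in each of seven groups. Table 5 in section 7.2.1 lists the single groups (15), all placebo recipients (21), the three prime-type pools (30), the two boost-type pools (45), all ALF43 recipients (75) and all vaccine recipients (105).

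Section 2.5 gives one arm a question of its own: "Group 7 will assess whether or not the concept of co-delivery of Env-C Plasmid DNA" and protein raises responses. On mucosal sampling, section 5.6.1 says: "Participants will have the option of participating in separately consented mucosal collections". Sections 5.6.1.1 and 5.6.1.2 offer cervicovaginal collection to women, semen collection to men and rectal sponges to both.

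Section 7.2.4 provides for a later SAP that may alter these choices.

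**The concern.** A Wald interval is a large-sample method. It uses a normal quantile although the standard deviation is estimated from the same data, and at n=15 that estimate is uncertain enough to matter. The section switches to exact or rank-based methods for proportions and tests, so the continuous interval is the one place where a large-sample rule is set without regard to group size.

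At stake is the honesty of the 95% label on the single-group immune summaries. Pooling helps six of the seven regimens, whose prime or boost type can be described in a larger set. It does not help Group 7, which is in neither the prime-type nor the boost-type pools. Group 7 is counted in the sets of 75 and 105, but those do not isolate its regimen.

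**Working it through.** **The plan's own figure.** The protocol gives a nominal level of 95% and no achieved coverage, so there is no coverage figure to reproduce. As a check on the group size, the n=15 exact intervals in Table 5 were recomputed and all agree (for example 2 of 15: 1.7% to 40.5%).

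**Inputs.**
- Set sizes: 15, 21 (7 × 3), 30, 45, 75 and 105 (sections 5.3 and 7.2.1). The 75 are groups 2, 4, 5, 6 and 7.
- Critical value: 1.96. This is the standard meaning of Wald; the protocol does not state it.
- Distribution: normal on the scale analysed. This is an assumption.

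**Formula.** The interval is x̄ ± 1.96·s/√n. It covers the true mean μ when |x̄ − μ|/(s/√n) < 1.96, and under normality that ratio follows a t distribution with n−1 degrees of freedom. So

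coverage = P(|t(n−1)| < 1.96), and the widening needed to reach 95% is t(0.975, n−1)/1.96.

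| n | Set | Wald coverage | t critical value | Widening with t |
|---|---|---|---|---|
| 15 | single vaccine group | 92.98% | 2.145 | 9.4% |
| 21 | placebo | 93.59% | 2.086 | 6.4% |
| 30 | prime-type pools | 94.03% | 2.045 | 4.4% |
| 45 | boost-type pools | 94.36% | 2.015 | 2.8% |
| 75 | any ALF43 | 94.62% | 1.993 | 1.7% |
| 105 | all vaccine | 94.73% | 1.983 | 1.2% |

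A simulation of log-scale data (200,000 samples per setting) gave 93.0%, 94.0% and 94.8% for Wald at n=15, 30 and 105, and 95.0% at each for t. If the standard deviation were computed with divisor n, coverage at n=15 would be 92.1%.

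**Seven groups together.** For one readout, the chance that at least one of seven independent single-group intervals misses is 1 − 0.9298^7 = 39.9%, against 1 − 0.95^7 = 30.2% with correct intervals. Only the difference, 39.9 − 30.2 = 9.7 points, comes from the Wald choice.

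**Mucosal subsets.** Semen and cervicovaginal samples each come from one sex and are optional, so n is below 15 in any group that includes both sexes. Uptake is not given. At an assumed n of 8 or 5, Wald coverage is 90.9% or 87.8%, and t widens the interval by 21% or 42%. Rectal sponges may come from both sexes, so a reduced n is not established for them.

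**If skewed readouts were summarised untransformed.** The protocol does not say they would be. With assumed log-normal data, simulated coverage of the arithmetic mean (200,000 samples per setting) is:

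| Assumed SD (log10) | Wald, n=15 | t, n=15 | Wald, n=105 |
|---|---|---|---|
| 0.3 | 88.5% | 90.5% | 93.5% |
| 0.5 | 80.4% | 82.5% | 90.1% |
| 0.8 | 62.7% | 64.7% | 77.6% |

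Here the scale is the problem; neither the t quantile nor pooling fully repairs it.

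**The case against.** The strongest reply is that the protocol states no critical value. If the analyst reads Wald with a t quantile, the shortfall vanishes, and the choice of quantile and scale is ordinary SAP detail that section 7.2.4 expressly leaves open. The first half is true but is not the usual reading. The second half covers what is left unsaid, such as the scale. It does not cover a named method that the text says will be used and that is a poor choice at n=15. If a t quantile was meant, the wording still needs correcting.

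A second reply is that nothing depends on these intervals. That stands. The study is hypothesis-generating, medians and ranges are also reported, group comparisons may use rank tests, and the primary safety intervals are exact. It caps the importance of the point.

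Third, the sentence on analysis sets follows the one on Mann-Whitney tests, so it speaks to comparisons; the protocol does not say which sets receive Wald intervals. That also stands. Applying the pools to the summaries is an inference, and it favours the plan, since the pooled coverage is nearly nominal.

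Finally, the untransformed and mucosal figures rest on assumed standard deviations and uptake, and most of the 39.9% would remain with perfect intervals. All of that is right. The conclusion rests on the 93.0% alone.

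**Conclusion.** The point holds and is minor. On the usual reading, the interval that section 7.2.3 prescribes covers 93.0% rather than 95% in a 15-person group, and 94.0% to 94.7% in the pooled vaccine sets. This assumes a quantile of 1.96 and roughly normal data on the scale analysed. The consequence is confined to descriptive immune summaries: those of the seven single groups, and most clearly Group 7, plus any smaller sex-specific mucosal subset. No test, sample size or safety conclusion changes.

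**What to change.** In section 7.2.3, or in the SAP if the protocol is not being amended, replace Wald with t-based 95% intervals for continuous immune readouts. This is a one-word change available in any standard software. The cost is wider intervals: 9.4% at n=15, falling to 1.2% at n=105, and more in small mucosal subsets.

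Separately, the SAP should name the scale for each readout. For positive, right-skewed readouts, log10 with geometric means is the natural choice; note that this summarises a geometric mean in place of an arithmetic one. Where zeros or negative values occur, an option is the exact interval for the median already being reported. At n=15 that runs from the 4th to the 12th ordered value, with coverage 1 − 2·P(Bin(15, 0.5) ≤ 3) = 96.5%. These are SAP options; the correction of the interval does not depend on them.

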2.6.2 SECONDARY

1. Determine whether the adjuvants under study improve the immunogenicity of the Env-C Plasmid DNA priming.
2. Determine whether the addition of ALF43 to the Rehydragel® -HIV Env gp145 C.6980 protein boost further improves the immune response to HIV Env gp145 C.6980 protein.
3. Determine whether adjuvants improve humoral responses across vaccination regimens.
4. Evaluate the influence of various adjuvants on cellular immune responses.
5. Describe mucosal humoral responses across vaccination regimens in cervicovaginal and rectal secretions and semen.

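### The pooled boost comparison is offered only an unstratified Mann-Whitney test; stratifying by prime would protect its power at almost no cost

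*Protocol*

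**What the plan says.** Section 7.2.3 of the Protocol states: "Comparisons of these endpoints between study groups may be made using non-parametric Mann-Whitney U tests". On which groups, it adds: "The groups will be the same as used for the safety comparison but also may include other groups". For continuous endpoints, "non-parametric Mann-Whitney U tests" are the only method named, with no stratification factor and no alternative.

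The safety groups are listed in Tables 5 and 6 of section 7.2.1. Besides the single groups they contain pooled prime sets, "DNA alone (1+2), DNA+TCI (3+4), DNA/ALF43 (5+6"), with 30 vaccinees each, and pooled boost sets, "HIV Env gp145 C.6980 /Rehydragel boost (1+3+5), HIV Env gp145 C.6980 /Rehydragel/ALF43 boost (2+4+6"), with 45 each.

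Table 1 (section 2.5) shows how these sets arise. Groups 1 to 6 cross three primes (DNA alone, DNA with dmLT, DNA with ALF43) with two boosts (protein with Rehydragel, without or with ALF43). Section 5.3 gives the cell size: "There will be 18 participants per group (15 vaccine recipients and 3 placebo recipients").

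Secondary objective 1 (section 2.6.2) is to "Determine whether the adjuvants under study improve the immunogenicity of the Env-C Plasmid DNA priming". Secondary objective 2 asks whether ALF43 added to the Rehydragel/protein boost improves the response further. Secondary endpoint 1 (sections 1.2.2 and 2.7.2) is read after the priming series. Boosts are given at weeks 20, 32 and 56. Section 7.2.4 says a later SAP will elaborate on the analysis and may change it.

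**The concern.** The comparison that uses all the data for objective 2 is 1+3+5 against 2+4+6. Each side holds 15 vaccinees from each of three primes. Objective 1 supposes that those primes differ, and the rabbit study in section 2.2.2 reports slower antibody induction with DNA plus dmLT, although all rabbit groups reached high titres.

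An unstratified rank test puts all 90 values into one ranking. The spread between primes then counts as random variation, although the design balances it across the two sides. The more the priming adjuvants succeed, the weaker the boost test becomes. At stake is a real ALF43 boost effect being missed in a trial with 15 vaccinees per cell.

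**Working it through.** **The plan's own figures.** The protocol states no power for any secondary comparison. The nearest figures for these group sizes are in Table 6, at a 10% event probability. With P(>0) = 1 − 0.9^n and P(>1) = 1 − 0.9^n − n × 0.1 × 0.9^(n−1):
- n = 15: 79.4% and 45.1%
- n = 30: 95.8% and 81.6%
- n = 45: 99.1% (printed as >99%) and 94.8%

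All agree with the table, which confirms the pooled sizes of 30 and 45.

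**Inputs.** From the protocol: 15 vaccinees per cell, the 3 × 2 layout and the pooled sets. Section 7.2.2 gives a two-sided 0.05 level for safety comparisons; it is assumed here for the secondary ones. Also assumed, because the documents give no values: normal data on the log scale with within-cell SD 1, a boost effect of 0.6 SD, a prime effect of 0.75 SD, and differences in the other factor from 0 to 3 SD.

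**Tests.** Both use the centred rank sum U = R − m(m+n+1)/2, with variance V = mn(m+n+1)/12.
- Unstratified: one ranking with m = n = 45, so V = 45 × 45 × 91/12 = 15,356.25.
- Van Elteren: rank within each prime with m = n = 15, so V = 15 × 15 × 31/12 = 581.25 per stratum. With weight 1/(15+15+1) = 1/31, the total variance is 3 × 581.25/31² = 1.8145.

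The pooled variance formula treats all 90 values as exchangeable. Because each side contains the same 15 per prime, the true null variance is smaller when primes differ. That is why the unstratified test becomes conservative.

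**Boost contrast, 45 v 45, 0.6 SD effect (20,000 simulated trials per row).** The second column shows the dilution: 0.6 divided by √(1 + variance of the prime means). For 0/1/2 this is 0.6/√(1 + 2/3) = 0.46.

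| Prime means (SD) | Diluted effect | Power, unstratified | Power, stratified | Loss (points) | Null size, unstratified / stratified |
|---|---|---|---|---|---|
| 0/0/0 | 0.60 | 78.5% | 77.6% | −0.9 | 4.9% / 4.7% |
| 0/0.25/0.5 | 0.59 | 77.0% | 77.4% | 0.4 | 4.4% / 4.8% |
| 0/0.5/0.5 | 0.58 | 76.5% | 77.2% | 0.7 | 4.6% / 5.0% |
| 0/0.5/1 | 0.56 | 74.0% | 78.1% | 4.1 | 3.7% / 5.1% |
| 0/1/1 | 0.54 | 70.3% | 76.6% | 6.3 | 3.1% / 5.1% |
| 0/1/2 | 0.46 | 56.2% | 77.2% | 21.0 | 0.9% / 4.6% |
| 0/1.5/3 | 0.38 | 31.3% | 77.2% | 45.9 | 0.1% / 5.2% |

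Simulation error is about √(0.77 × 0.23/20,000) = 0.3 points per power figure.

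**Prime contrast, 30 v 30, 0.75 SD effect.**

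| Boost difference (SD) | Unstratified | Stratified by boost |
|---|---|---|
| none (after priming, before week 20) | 79.4% | 79.3% |
| 0.5 | 77.0% | 78.8% |
| 1 | 71.3% | 79.2% |
| 2 | 45.4% | 79.1% |

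The first row is the situation of secondary endpoint 1: until week 20, Groups 1 and 2 have had the same treatment, as have 3 and 4, and 5 and 6. The other rows apply only to comparisons made after boosting.

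**The case against.** The wording is permissive. The protocol allows Mann-Whitney tests without requiring them, admits other groups, calls the work hypothesis-generating and lets the SAP make changes. Nowhere does it state a test of 1+3+5 against 2+4+6; that contrast follows from reading 7.2.3 together with Tables 5 and 6. Comparing 1 v 2, 3 v 4 and 5 v 6 is equally open and holds the prime constant, although with only 15 v 15 each time. No power target is set, so no stated claim fails. The large losses need prime differences of 2 to 3 SD that persist after protein boosting.

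All of this stands, and it limits the point to a conditional one about efficiency. It does not remove it. The protocol does name a test and does carry over pooled groups, and the two fit poorly together; a SAP author would start from that pairing.

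A reader might infer that both main secondary objectives lose power. The documents do not support this. Secondary endpoint 1 is read before any boost, when there is no boost factor to leave out. Its wording contains a stray word that may hint at a second time point, but none is stated. A reader might also infer a false-positive risk. There is none from this source: the size of the unstratified test falls below 5%.

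**Conclusion.** The point holds in a limited form. If the pooled boost sets are compared with the only test that section 7.2.3 names, power for secondary objective 2 depends on how far the primes differ. Under the assumed 0.6 SD boost effect, the loss is about 0 to 1 point for prime differences up to 0.5 SD, about 4 to 6 points when the largest is 1 SD, and about 21 points at 0/1/2 SD. The last row of the boost table marks an extreme and should not carry the argument.

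Pooled prime contrasts share the problem only after week 20. The comparison after priming and before boosting is unaffected. The sizes rest on assumed normal log-scale data and assumed effects. The direction does not depend on the particular values chosen: leaving out a balanced factor that matters makes this test conservative.

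**What to change.** State in section 7.2.3, or carry into the SAP, that:
- the pooled boost contrast (1+3+5 v 2+4+6) uses a van Elteren (stratified Wilcoxon) test stratified by prime regimen;
- any pooled prime contrast (1+2, 3+4, 5+6) made after boosting starts is stratified by boost regimen;
- the post-prime, pre-boost comparison of secondary endpoint 1 may stay unstratified.

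This changes analysis wording only. It uses group labels already assigned and keeps the non-parametric approach. The cost is about 1 point of power if the other factor has no effect (78.5% to 77.6% for the boost contrast).

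One limit remains. Section 5.3 enrols Group 1 in full before Groups 2 to 7, so sets containing Group 1 are not fully concurrent with their comparators. Stratifying by prime does not cure that.
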